To evaluate the efficacy of Ad26.COV2.S in the prevention of molecularly confirmed a moderate to severe/critical COVID-19 b as compared to placebo, with onset 1 day after study vaccination	First occurrence of molecularly confirmed a , moderate to severe/critical COVID-19 b with onset 1 day after double-blind vaccination
To assess the effect of Ad26.COV2.S on COVID-19 requiring medical intervention (based on objective criteria) compared to placebo	
 
First occurrence of COVID-19 requiring medical intervention (such as a composite endpoint of hospitalization, ICU admission, mechanical ventilation, and ECMO, linked to objective measures such as decreased oxygenation, X-ray or CT findings) and linked to any molecularly confirmeda, COVID-19b,c at least 14 days after double-blind vaccination (Day 15)
 
First occurrence of COVID-19 requiring medical intervention and linked to any molecularly confirmeda, COVID-19b,c at least 28 days after double-blind vaccination (Day 29)
 

To assess the effect of Ad26.COV2.S on SARS-CoV-2 viral ribonucleic acid (RNA) load compared to placebo for moderate to severe/critical COVID-19 b	Assessment of the SARS-CoV-2 viral load by quantitative reverse-transcriptase polymerase chain reaction (RT-PCR), in participants with molecularly confirmed a , moderate to severe/critical COVID-19 b by serial viral load measurements during the course of a COVID-19 episode
To assess the effect of Ad26.COV2.S on molecularly confirmed a mild COVID-19 c	
 
First occurrence of molecularly confirmeda, mild COVID-19c, at least 14 days after double-blind vaccination (Day 15)
 
First occurrence of molecularly confirmeda, mild COVID-19c, at least 28 days after double-blind vaccination (Day 29)
 

Objectives	Endpoints

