## Hypotheses

The study is designed to test the co-primary hypotheses of vaccine efficacy (VE) in the PP population. For both co-primary endpoints, the following hypothesis will be tested:

H0: VE  $\leq$ 30% versus H1: VE >30% and each hypothesis will be evaluated at a 2.5% one-sided significance level.

[figure not shown]
The co-primary endpoints will evaluate

- the first occurrence of molecularly confirmed, moderate to severe/critical COVID-19 according to the case definition, with onset at least 14 days after double-blind vaccination with Ad26.COV2.S versus placebo, in the PP population, including all events from both age groups, with and without comorbidities.
- the first occurrence of molecularly confirmed, moderate to severe/critical COVID-19 according to the case definition, with onset at least 28 days after double-blind vaccination with Ad26.COV2.S versus placebo, in the PP population, including all events from both age groups, with and without comorbidities.

If testing for both primary endpoint hypotheses is successful, secondary objectives will be evaluated against a null hypothesis employing a lower limit VE>0%. The method to perform hypothesis testing of primary and secondary objectives preserving the FWER will be specified in the SAP. The FWER will be controlled at 2.5% one-sided significance level.

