### Sample Size Calculation

#### *Efficacy (Total Sample Size)*

The study target number of events (TNE) is determined using the following assumptions:

- a VE for molecularly confirmed, moderate to severe/critical SARS-CoV-2 infection of 60%.
- approximately 90% power to reject a null hypothesis of  $H_0: VE \leq 30\%$ .
- type 1 error rate  $\alpha = 2.5\%$  to evaluate VE of the vaccine regimen (employing the sequential probability ratio test [SPRT] to perform a fully sequential design analysis; detailed in the methods section).
- a randomization ratio of 1:1 for active versus placebo.

Events for the co-primary endpoints are defined as first occurrence of molecularly confirmed, moderate to severe/critical COVID-19 according to the case definition (see above) in the Per-protocol Efficacy

population at least 14 days after double-blind vaccination (Day 15) and at least 28 days after double-blind vaccination (Day 29) with study vaccine.

Under the assumptions above, the TNE to compare the active vaccine versus placebo equals 154, based on events in each active vaccination and placebo group, according to the primary endpoints case definition of moderate to severe/critical COVID-19.

If the primary hypotheses testing is successful, secondary objectives will be evaluated against a null hypothesis employing a lower limit  $VE > 0\%$ . The method to perform hypothesis testing of primary and secondary objectives preserving the FWER will be specified in the SAP. The FWER will be controlled at 2.5%.

Further details on the sample size calculation are provided in the body of the protocol.

The operating characteristics of the study design, statistical methods, study monitoring rules and efficacy evaluation specified in this protocol with the chosen event and sample sizes will be described in a separate modeling and simulation report and will be added to the SAP before the first participant is vaccinated.

No additional participants will be recruited for the open-label phase.

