### 3. OBJECTIVES AND ENDPOINTS

#### 3.1. Double-blind Phase of the Study

Objectives	Endpoints
Co-Primary	
To demonstrate the efficacy of Ad26.COV2.S in the prevention of molecularly confirmed a , moderate to severe/critical COVID-19 b , as compared to placebo, in SARS-CoV-2 seronegative adults	
 
First occurrence of molecularly confirmeda, moderate to severe/critical COVID-19b, with onset at least 14 days after double-blind vaccination (Day 15)
 
First occurrence of molecularly confirmeda, moderate to severe/critical COVID-19b, with onset at least 28 days after double-blind vaccination (Day 29)
 

Secondary ( The method used to perform hypothesis testing preserving the family-wise error rate [FWER] will be specified in the Statistical Analysis Plan [SAP] )	
Efficacy	
To demonstrate the efficacy of Ad26.COV2.S in the prevention of molecularly confirmed a , severe/critical COVID-19 b , as compared to placebo	
 
First occurrence of molecularly confirmeda, severe/critical COVID-19b, with onset at least 14 days after double-blind vaccination (Day 15)
 
First occurrence of molecularly confirmeda, severe/critical COVID-19b, with onset at least 28 days after double-blind vaccination (Day 29)
 

To demonstrate the efficacy of Ad26.COV2.S in the prevention of molecularly confirmed a , moderate to severe/critical COVID-19 b , as compared to placebo, in adults regardless of their serostatus	
 
First occurrence of molecularly confirmeda, moderate to severe/critical COVID-19b, with onset 1 day after double-blind vaccination
 
First occurrence of molecularly confirmeda, moderate to severe/critical COVID-19b, with onset 14 days after double-blind vaccination (Day 15)
 
First occurrence of molecularly confirmeda, moderate to severe/critical COVID-19b, with onset at least 28 days after double-blind vaccination (Day 29)
 

Objectives	Endpoints

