To evaluate the efficacy of Ad26.COV2.S in the prevention of molecularly confirmed a moderate to severe/critical COVID-19 b as compared to placebo, with onset 1 day after study vaccination	First occurrence of molecularly confirmed a , moderate to severe/critical COVID-19 b with onset 1 day after double-blind vaccination
To assess the effect of Ad26.COV2.S on COVID-19 requiring medical intervention (based on objective criteria) compared to placebo	
 
First occurrence of COVID-19 requiring medical intervention (such as a composite endpoint of hospitalization, ICU admission, mechanical ventilation, and ECMO, linked to objective measures such as decreased oxygenation, X-ray or CT findings) and linked to any molecularly confirmeda, COVID-19b,c at least 14 days after double-blind vaccination (Day 15)
 
First occurrence of COVID-19 requiring medical intervention and linked to any molecularly confirmeda, COVID-19b,c at least 28 days after double-blind vaccination (Day 29)
 

To assess the effect of Ad26.COV2.S on SARS-CoV-2 viral RNA load compared to placebo for moderate to severe/critical COVID-19 b	Assessment of the SARS-CoV-2 viral load by quantitative RT-PCR, in participants with molecularly confirmed a , moderate to severe/critical COVID-19 b by serial viral load measurements during the course of a COVID-19 episode
To assess the effect of Ad26.COV2.S on molecularly confirmed a , mild COVID-19 c	
 
First occurrence of molecularly confirmeda, mild COVID-19c, at least 14 days after double-blind vaccination (Day 15)
 
First occurrence of molecularly confirmeda, mild COVID-19c, at least 28 days after double-blind vaccination (Day 29)
 

To assess the effect of Ad26.COV2.S on COVID-19 as defined by the US FDA harmonized case definition d	
 
First occurrence of molecularly confirmeda COVID-19d at least 14 days after double-blind vaccination (Day 15)
 
First occurrence of molecularly confirmeda COVID-19d at least 28 days after double-blind vaccination (Day 29)
 

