In a subset of participants, to evaluate the safety and reactogenicity in terms of solicited local and systemic AEs during the 7 days after double-blind vaccination, and in terms of unsolicited AEs during the 28 days after double-blind vaccination	Occurrence, intensity, duration and relationship of solicited local and systemic AEs during the 7 days following vaccination and of unsolicited AEs during the 28 days after double-blind vaccination
Immunogenicity	Analysis of antibodies binding to the SARS-CoV-2 S protein by ELISA
Exploratory	
To evaluate the long term durability of the efficacy of Ad26.COV2.S in the prevention of molecularly confirmeda, moderate to severe/critical COVID-19b, defined as having an onset of at least:
 
 
• 1 day after Ad26.COV2.S
 
• 14 days after Ad26.COV2.S
 
• 28 days after Ad26.COV2.S.
 

To assess the effect of Ad26.COV2.S on occurrence of confirmed asymptomatic or undetected infections with SARS-CoV-2, as compared to placebo from Day 1 to Day 29	Serologic conversion between baseline (Day 1; pre-vaccination) and Day 29 after double-blind vaccination using an ELISA and/or SARS-CoV-2

Objectives	Endpoints
	immunoglobulin assay that is dependent on the SARS-CoV-2 nucleocapsid (N) protein
To assess the effect of Ad26.COV2.S on SARS-CoV-2 viral RNA load compared to placebo for mild COVID-19 c	Assessment of the SARS-CoV-2 viral load by quantitative RT-PCR, in participants with molecularly confirmed a mild COVID-19 c by serial viral load measurements during the course of a COVID-19 episode
To assess the effect of Ad26.COV2.S on health care utilization (such as hospitalization, ICU admission, ventilator use) linked to any molecularly confirmed a COVID-19, as compared to placebo	
 
Health care utilization (such as hospitalization, ICU admission, ventilator use) linked to any molecularly confirmeda COVID-19 at least 14 days after double-blind vaccination (Day 15)
 
Health care utilization (such as hospitalization, ICU admission, ventilator use) linked to any molecularly confirmeda COVID-19 at least 28 days after double-blind vaccination (Day 29)
 

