	
Adenovirus neutralization as measured by VNA
 
Analysis of antibodies to S and the receptor-binding domain (RBD) of the SARS-CoV-2 S protein
 
Original and/or emerging SARS-CoV-2 virus lineage neutralization as measured by virus neutralization assay (VNA; wild-type virus and/or pseudovirion expressing SARS-CoV-2 S protein)
 
Passive transfer: analysis of immune mediators correlating with protection against experimental SARS-CoV-2 challenge in a suitable animal model.

To explore changes in the SARS-CoV-2 genome	Development of SARS-CoV-2 variants
To examine efficacy for moderate/severe and severe disease as well as medical utilization or death in the vaccine and placebo groups for variant strains that have been identified	Occurrence of moderate/severe or severe COVID-19, medical utilization, or death for each of the circulating viral variants, identified by S-gene sequencing
To evaluate patient-reported outcomes (PROs) in relation to the presence of SARS-CoV-2 infection and the presence, severity and duration of COVID-19 signs and symptoms in participants who received Ad26.COV2.S, as compared to placebo	Presence, severity and duration of COVID-19 signs and Symptoms; Confirmation of SARS-CoV-2 infection by molecular testing
To assess the difference in severity of cases in participants who received Ad26.COV2.S as compared to placebo	Reduction in severity of COVID-19 signs and Symptoms
To assess the impact of pre-existing humoral immunity against coronaviruses other than SARS-CoV-2 at baseline on Ad26.COV2.S vaccine immunogenicity	Analysis of antibodies binding to coronaviruses other than SARS-CoV-2 by ELISA
To assess the incidence of co-infection of COVID-19 and other respiratory pathogens and to assess the effect of the vaccine during such co-infections as well as to estimate the incidence of other respiratory pathogens during the study period.	Analysis of broad respiratory pathogens panel in the nasal swabs collected during a confirmed COVID-19 episode and in a subset of nasal swab samples from participants with a symptomatic infection.

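### The secondary viral-load objective claims a vaccine effect against placebo but compares only participants who became moderate to severe/critical cases, so selection alone can produce a false benefit or harm

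*Protocol*

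**What the plan says.** Protocol Section 3.1 and the synopsis (Section 1.1) list among the secondary efficacy objectives: "To assess the effect of Ad26.COV2.S on SARS-CoV-2 viral RNA load compared to placebo for moderate to severe/critical COVID-19". The endpoint is "Assessment of the SARS-CoV-2 viral load by quantitative RT-PCR, in participants with molecularly confirmed" moderate to severe/critical COVID-19, "by serial viral load measurements during the course of a COVID-19 episode". No value exists for anyone who did not become such a case. Section 4.1 likewise confines viral load to confirmed cases.

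The event that admits a participant to this comparison is the co-primary outcome. The co-primary objective begins "To demonstrate the efficacy of Ad26.COV2.S in the prevention of molecularly confirmed" and names the same moderate to severe/critical disease. The sample size section of the synopsis assumes "a VE for molecularly confirmed, moderate to severe/critical SARS-CoV-2 infection of 60" per cent.

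Two exploratory objectives in Section 3.1 have the same structure: "To assess the effect of Ad26.COV2.S on SARS-CoV-2 viral RNA load compared to placebo for mild COVID-19" and "To assess the difference in severity of cases in participants who received Ad26.COV2.S as compared to placebo".

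The Hypotheses paragraph of the synopsis adds that, once both co-primary tests succeed, "secondary objectives will be evaluated against a null hypothesis employing a lower limit VE>0" per cent. It does not say which secondary objectives this covers.

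**The concern.** The wording promises a causal contrast between randomised arms, but the endpoint population is chosen by an outcome that the vaccine changes. Vaccine-arm cases are those the vaccine did not prevent. Placebo-arm cases also include those it would have prevented. If these two kinds of case differ in viral load, the arms differ even when the vaccine has no effect on load in anyone. Section 4.2 gives balance of known and unknown attributes as the reason for randomising; that balance does not carry over to a comparison among cases.

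If prevented cases tend to have low load, breakthrough cases look worse and a real reduction may be hidden. If they tend to have high load, a benefit appears where there is none. Either result could be reported under a named secondary efficacy objective as the effect of the vaccine.

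**Working it through.** **Inputs from the synopsis sample size section:** VE 60%, null VE 30%, one-sided alpha 2.5%, about 90% power, 1:1 allocation, 154 events. The protocol gives no figure for viral load. The correlation r, the difference d and the SD below are assumptions, shown over a range.

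**1. The plan's event count.** With 1:1 allocation, the expected share of cases on vaccine is (1−VE)/(2−VE).
- Under the null: 0.7/1.7 = 0.4118. Under VE 60%: 0.4/1.4 = 0.2857.
- Normal approximation: [(1.960·√(0.4118·0.5882) + 1.282·√(0.2857·0.7143)) / (0.4118−0.2857)]² = 149.95 events.
- Exact binomial at 154 events: reject if 51 or fewer cases are on vaccine; alpha 0.0246, power 0.908.

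These are fixed-sample checks of a sequential design. They agree with 154, which is not in question.

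**2. Who is compared.** At 154 events and VE 60%, 154 × 0.2857 = 44 vaccine cases and 110 placebo cases. If the vaccine causes no cases, 60% of the placebo cases, 0.6 × 110 = 66, have no vaccine counterpart.

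**3. Precision.** The SE of the difference in mean load is √(1/44 + 1/110) = 0.178 SD. The difference detectable with 80% power (two-sided 5%) is 2.80 × 0.178 = 0.50 SD.

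**4. Spurious shift under no true effect on load.** Let a latent normal variable decide which 40% of would-be placebo cases still become cases under vaccine, with correlation r to load. The mean of the top 40% of a standard normal is φ(0.253)/0.4 = 0.966, so the shift is 0.966·r SD.

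| assumed r | shift (SD) | share of 0.50 SD | rejection, nominal two-sided 5% |
|---|---|---|---|
| 0 | 0 | 0% | 5% |
| 0.1 | 0.10 | 19% | 8.4% |
| 0.2 | 0.19 | 39% | 19.1% |
| 0.3 | 0.29 | 58% | 36.9% |

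A negative r gives the same sizes in the direction of false benefit. The extreme, selection entirely on load, is ±0.97 SD.

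**5. Second route.** Let d be the mean load of prevented minus non-prevented placebo cases. The placebo mean is a 60:40 mix of the two kinds and the vaccine mean is the non-prevented kind alone, so the apparent difference is −0.6·d.
- d = ±0.5 log10 gives ∓0.30 log10; d = ±1 gives ∓0.60.
- In 20,000 simulated trials per scenario (Welch t-test, two-sided 5%, SD 1.5 log10), false rejection is about 20% at |d| = 0.5 and about 59% at |d| = 1.
- Over SD 1.0 to 2.0 the ranges are 13–37% and 38–90%.
- At d = 0 it stays at about 5%.

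**The case against.** **No test is specified in the text reviewed.** It gives an objective, a population and a measurement, but no summary measure. Section 9.5.2 and the SAP were not available and may contain a suitable analysis. This stands: no missing method is alleged. The population and the word effect are nevertheless fixed in the protocol, and a model fitted to cases alone does not restore the randomised contrast.

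**The conditioning is disclosed.** The objective names moderate to severe/critical disease. That also stands; the fault is presenting the result as an effect of the vaccine.

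**The VE>0% null.** A reader might infer that viral load is in the formally tested set. The documents do not support that. Safety and immunogenicity objectives stand under the same secondary heading, yet the synopsis says no formal testing of either is planned, so the sentence cannot cover every secondary item. The testing strategy is left to the SAP. What remains is that nothing shown says viral load is outside the set, and a VE null has no meaning for a difference in load among cases.

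**The comparator.** A reader might take it to be all placebo infections. It is not: both arms are restricted to moderate to severe/critical cases, and the 60% refers to that outcome.

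**An all-participant score.** Giving non-cases zero looks like a repair, but it mainly re-tests VE. The expected counts alone give (110−44)/√154 = 5.3 standard errors, so it would nearly always signal an effect on load when there is none.

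**The sizes are assumed.** Neither r, d nor the SD comes from the documents. The figures show what is possible, not what occurred.

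**Timing.** Amendment 7 states that the final double-blind analyses are complete. Rewording now cannot change what was prespecified for them.

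**Conclusion.** The point holds as one about the claim attached to this endpoint. A comparison of about 44 breakthrough cases with about 110 placebo cases of the same severity is not a randomised comparison and should not be read as the vaccine's effect on viral load.

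Under no true effect, the spurious shift is 0.10 to 0.29 SD and the false rejection rate 8% to 37% for assumed correlations of 0.1 to 0.3; both routes show no bias when prevented and non-prevented cases have the same mean load. The calculation assumes that the vaccine causes no cases, that VE is 60% and that there are 154 cases. Direction and actual size cannot be settled from the documents.

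The two exploratory objectives share the problem but carry less weight. The co-primary and other first-occurrence endpoints, and the 154 events, are untouched.

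**What to change.** - In Sections 1.1 and 3.1, reword the secondary objective as a descriptive comparison of viral load in moderate to severe/critical cases by vaccine group. Use the same form for the exploratory mild-case and severity-of-cases objectives.
- State beside the Hypotheses paragraph that the VE>0% null does not apply to viral load among cases.
- Before any vaccine effect on load is claimed, report beside the case-only difference either principal-stratum bounds (participants who would be cases under either assignment) or a sensitivity analysis over a stated range of selection.
- Do not substitute a score that gives non-cases zero as the test of an effect on load.

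The cost is wording plus one extra analysis on data already collected, with no new visits or samples. The case-only result loses its status as an effect claim. Because the double-blind analyses are reported as complete, any bounds added now should be labelled post hoc unless the SAP already specifies them.

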## HYPOTHESES

The study is designed to test the co-primary hypotheses of VE in the per-protocol (PP) population. For both co-primary endpoints the following hypothesis will be tested:

H0: VE  $\leq$ 30% versus H1: VE  $>$ 30% and each hypothesis will be evaluated at a 2.5% one-sided significance level.

The co-primary endpoints will evaluate:

- the first occurrence of molecularly confirmed, moderate to severe/critical COVID-19 according to the case definition (Section 8.1.3.1), with onset at least 14 days after double-blind vaccination with Ad26.COV2.S versus placebo, in the PP population, including all events from both age groups, with and without comorbidities.
- the first occurrence of molecularly confirmed, moderate to severe/critical COVID-19 according to the case definition (Section 8.1.3.1), with onset at least 28 days after double-blind vaccination with Ad26.COV2.S versus placebo, in the PP population, including all events from both age groups, with and without comorbidities.

If testing for both primary endpoint hypotheses are successful, secondary objectives will be evaluated against a null hypothesis employing a lower limit VE $>$ 0%. The method to perform hypothesis testing of primary and secondary objectives preserving the FWER will be specified in the SAP. The FWER will be controlled at 2.5%.

Details are described in Section 9.

### 3.2. Open-label Active Phase

#### 3.2.1. Open-label Cross-over Phase

Participants will enter the open-label cross-over phase on the day that the participant received the cross-over vaccination or are unblinded until the day that the participant completed the booster visit. There are 2 main cohorts in the open label phase:

- Early vaccinated cohort: participants who were initially randomized to the Ad26.COV2.S group and received 1 dose of Ad26.COV2.S at day 1 in the trial
- Late vaccinated cohort: participants who were initially randomized to the placebo group and who received 1 dose of Ad26.COV2.S after unblinding

The main objective of the open-label phase of the study is to evaluate the COVID-19 outcomes after an early vaccination and after a late vaccination. Efficacy evaluations may be performed if feasible, ie, if pre-specified criteria are met, and will be specified in the SAP.

The exploratory objectives and endpoints for the open-label phase of the study are:

Objectives	Endpoints
The secondary safety objective of the double-blind phase	See double-blind endpoint
To evaluate molecularly confirmed a , symptomatic COVID-19 b	Incidence of symptomatic COVID-19 cases starting at 28 days after last vaccination
To evaluate molecularly confirmed a , severe/critical COVID-19 b	Incidence of severe/critical COVID-19 cases starting at 28 days after last vaccination
To evaluate confirmed a COVID-19 b requiring medical intervention (based on objective criteria)	Incidence of COVID-19 cases requiring medical intervention, starting at 28 days after last vaccination
To evaluate COVID-19 related death	Incidence of COVID-19 related deaths starting at 28 days after last vaccination
To describe the severity of breakthrough infections	The severity of COVID-19 cases may be evaluated by the severity and number of symptoms (severity) of COVID-19 cases, ratio of severe/critical COVID-19 cases and ratio of long COVID-19 cases (duration of more than 28 days)
To estimate potential correlate of risk/efficacy in relation to the primary endpoint of the main study and serious disease, hospitalization, and death based on immune responses in breakthrough cases compared to non-infected participants.	Levels of immune responses (antibody titers) and RNA sequencing analysis as available for participants having COVID-19 compared to non-infected participants.

a Molecularly confirmed COVID-19 is defined as a positive SARS-CoV-2 viral RNA result by a central laboratory using a RT-PCR based or other molecular diagnostic test.

b Per case definition for moderate to severe/critical COVID-19 as determined by the Clinical Severity Adjudication Committee (see below).

